16. CHANGES TO THE STATISTICAL ANALYSES SECTION OF THE PROTOCOL

As there were no subjects enrolled from Japanese sites, the randomization stratification factor “country of enrollment (ie, Japan versus ROW)” will not be used when the analysis is performed.

Frequency cross-tabulations of RBC transfusion dependent status for 84 days at baseline versus on treatment will not be provided.

The end date of the evaluation period defined in Section 10.1 is used as the censoring date when calculating the duration of RBC transfusion independence ≥ 56 days and ≥ 84 days, duration of RBC transfusion reduction and duration of platelet transfusion independence. As defined in Section 10.1, the days after a subject started subsequent MDS treatment will not be included in the response duration. The end date of the evaluation period defined in Section 10.1 is also used as the censoring date for subjects who do not achieve the corresponding response during the treatment period in the analysis of time to RBC transfusion independence ≥ 56 days and ≥ 84 days, and time to platelet transfusion independence.

Progression to AML will be identified based on documentations in central lab report or Follow-up Status CRF, please see detail in Section 10.2.8.

No other changes to the statistical analyses section of the protocol are made in this SAP.

18. APPENDICES

18.1. Appendix A: Date Imputation Guideline

18.1.1. Impute Missing AE/ Prior or Concomitant Medications

Incomplete Start Date:

Missing day and month

- If the year is **same** as the year of first day on study medication, then the day and month of the start date of study medication will be assigned to the missing fields
- If the year is **prior to** the year of first day on study medication, then December 31 will be assigned to the missing fields.
- If the year is **after** the year of first day on study medication, then January 1 will be assigned to the missing fields.

Missing day only

- If the month and year are **same** as the year and month of first day on study medication, then the start date of study medication will be assigned to the missing day.
- If the month and year are **before** the year and month of first day on study medication, then the last day of the month will be assigned to the missing day.
- If the month and year are **after** the year and month of first day on study medication, then the first day of the month will be assigned to the missing day.
- If the stop date is non-missing and the imputed start date is after the stop date, the start date will be imputed by the stop date.

Missing day, month, and year

- No imputation is needed, the corresponding AE will be included as TEAE.

Incomplete Stop Date: If the imputed stop date is before the start date then the imputed stop date will be equal to the start date.

Missing day and month

- If the year of the incomplete stop date is the **same** as the year of the last dose date of study medication, then the day and month of the last dose date will be assigned to the missing fields.
- If the year of the incomplete stop date is **prior to** the year of the last dose date of double-blind study medication, then December 31 will be assigned to the missing fields.
- If the year of the incomplete stop date is **after** the year of the last dose date of study medication, then January 1 will be assigned to the missing fields.

Missing day only

- If the month and year of the incomplete stop date are the **same** as the month and year of the last dose date of study medication, then the day of the last dose date will be assigned to the missing day.
- If the month and year of the incomplete stop date are **before** the month and year of the last dose date of the study medication, then the last day of the month will be assigned to the missing day.
- If the month and year of the incomplete stop date are **after** the month and year of the last dose date of study medication, then the first day of the month will be assigned to the missing day.

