11 ADVERSE EVENTS

11.1 Monitoring, Recording and Reporting of Adverse Events

An AE is any noxious, unintended, or untoward medical occurrence that may appear or worsen in a subject during the course of a study. It may be a new intercurrent illness, a worsening concomitant illness, an injury, or any concomitant impairment of the subject's health, including laboratory test values (as specified by the criteria below), regardless of etiology. Any worsening (ie, any clinically significant adverse change in the frequency or intensity of a pre-existing condition) should be considered an AE. A diagnosis or syndrome should be recorded on the AE page of the CRF rather than the individual signs or symptoms of the diagnosis or syndrome.

An overdose, accidental or intentional, whether or not it is associated with an AE, or abuse, withdrawal, sensitivity or toxicity to an IP should be reported as an AE. If an overdose is associated with an AE, the overdose and AE should be reported as separate terms.

All subjects will be monitored for AEs during the study. Assessments may include monitoring of any or all of the following parameters: the subject's clinical symptoms, laboratory, pathological, radiological or surgical findings, physical examination findings, or other appropriate tests and procedures.

All AEs will be recorded by the Investigator from the time the subject signs informed consent to 28 days after the last dose of IP or until the last study visit, whichever period is longer. Adverse events and SAEs will be recorded on the AE page of the CRF and in the subject's source documents. All SAEs must be reported to Celgene Drug Safety within 24 hours of the investigator's knowledge of the event by facsimile, or other appropriate method, using the SAE Report Form, or approved equivalent form.

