5.1.1. Dates Handling

Dates will be stored as numeric variables in the SAS analysis files and reported in DDMMYYYY format (i.e., the Date9. datetime format in SAS). Dates in the clinical database are classified into the categories of procedure dates, log dates, milestone dates, outcome dates, and special dates.

- **Procedure Dates** are the dates on which a given protocol-specified procedure are performed. They include the dates of laboratory testing, physical examinations, tumor scans, etc. They should be present whenever data for a protocol-specified procedure is present and should only be missing when a procedure is marked as “NOT DONE” in the database. Procedure dates will not be imputed.
- **Log Dates** are dates recorded in case report form (CRF) data logs. Specifically, they are the start and end dates for adverse events and concomitant medications/procedures. They should not be missing unless an event or medication is marked as *ongoing* in the database. Otherwise, incomplete log dates will be imputed according to the rules in [Appendix A](#). However, in listings, log dates will be shown as recorded without imputation.
- **Milestone Dates** are dates of protocol milestones such as randomization, study drug start date, study termination, etc. They should not be missing if the milestone occurs for a subject. They will not be imputed.
- **Outcome Dates** are dates corresponding to study endpoints such as survival, progression, etc. In most cases they are derived either from a milestone (e.g., the survival date is derived from the death date), or a procedure date (e.g., the progression date is derived from the date of the tumor scan that was used to determine

progression). They may be subject to endpoint-specific censoring rules if the outcome did not occur but are not otherwise subject to imputation.

- **Special Dates** cannot be classified in any of the above categories and they include the date of birth. They may be subject to variable-specific censoring and imputation rules (see Section 5.1.2).

Dates recorded in comment fields will not be imputed or reported in any specific format.

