8.10. Concomitant Medications

Concomitant medications are defined as non-study medications that are started after the initiation but before the end of the study treatment (last dose of study drug + 28 days, death, whichever earlier), or started before the initiation of the study treatment and ended or remain ongoing after the study treatment initiation. Concomitant medications will be coded in WHO drug dictionary (March 2018 version, or higher). Medication not in the WHO drug dictionary will be classified as “Not Coded” in the analysis.

The ATC coding scheme of the WHO will be used to group medications into relevant categories. A frequency table by ATC class and preferred name will be provided. All concomitant medications documented on the CRF will be listed for the ITT population.

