11.1. Adverse Events

Adverse events (AEs) will be coded according to the MedDRA version 21.0 or higher. The severity of AEs will be assessed by the investigator according to the Common Terminology Criteria for Adverse Events (CTCAE) version 4.0. For any AE not listed in the CTCAE grading system, the severity of these events will be assessed by the Investigator using a 5-point scale as described in Section 11.2.2. of the protocol.

Treatment-emergent adverse events (TEAEs) are defined as any AE occurring or worsening with an onset date on or after the date of the first dose of the study medication and within 28 days after the date of the last dose. AEs will be summarized by SOC, preferred term (PT) and treatment group. The AE summaries will include incidence tables of:

- Summary of TEAEs.
- TEAEs.
- Treatment-related TEAEs.
- Serious TEAEs.
- Treatment-related serious TEAEs.
- TEAEs with CTCAE toxicity grade of 3 or 4.
- Treatment-related TEAEs with CTCAE toxicity grade of 3 or 4.
- Serious TEAEs with severity of grade 3 or 4.
- Treatment-related Serious TEAEs with severity of grade 3 or 4.
- TEAE leading to death.
- TEAEs leading to dose reduction.
- TEAEs leading to dose interruption.
- TEAEs leading to dose interruption and reduction.
- TEAEs leading to treatment discontinuation.
- Treatment-related TEAEs leading to death.
- TEAEs by maximum severity.
- TEAEs by age group (<65, 65 to 74, ≥75 years).
- TEAEs by sex.
- TEAEs by decreasing order of frequency of preferred term.

- TEAEs by decreasing order of frequency of system organ class.
- Serious TEAEs by decreasing order of frequency of preferred term.
- Serious TEAEs by decreasing order of frequency of system organ class
- Pre-treatment AEs.
- Non-serious TEAEs

Subjects with multiple events reported for the same preferred term will be counted only once per SOC and PT level. For summaries by severity (CTCAE grade), if a subject experience the same PT multiple events, then the subject will be counted only once and for the greatest severity.

In summaries of treatment-related TEAEs, if a subject reports multiple occurrences of the same AE, only the treatment-related occurrence will be summarized. Adverse events with missing relationship to study medication will be imputed as related to study medication.

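### SAP 18.1.1 checks an imputed start against a known stop date only when the day alone is missing, so some adverse events that ended before first dose are counted as treatment-emergent

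*SAP*

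**What the plan says.** SAP 5.1.1 classes AE and concomitant medication/procedure dates as log dates and sends the incomplete ones to Appendix A: "Otherwise, incomplete log dates will be imputed according to the rules in" that appendix. SAP 18.1.1 then gives three cases for an incomplete start date.

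- **Day and month missing.** If the year is that of first dose, "then the day and month of the start date of study medication will be assigned to the missing fields". An earlier year is completed with 31 December and a later year with 1 January. The stop date is not mentioned.
- **Day missing.** There are similar rules by month, followed by a check: "If the stop date is non-missing and the imputed start date is after the stop date", the start is set to the stop date.
- **Whole date missing.** "No imputation is needed, the corresponding AE will be included as TEAE". Nothing is said about the stop date, or about medications.

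The stop-date half of 18.1.1 puts its own consistency rule in the heading: "If the imputed stop date is before the start date then the imputed stop date will be equal to the start date".

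SAP 11.1 takes a treatment-emergent AE (TEAE) to be "any AE occurring or worsening with an onset date on or after the date of the first dose of the study medication"; the window closes 28 days past the last dose. SAP 8.7 classes a medication as prior if it began before the first-dose date. SAP 8.10 defines concomitant medications as "non-study medications that are started after the initiation but before the end of the study treatment", or as begun earlier and ended or still running after treatment starts.

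**The concern.** A stop date before first dose settles the question that the imputation is meant to answer: the event or medication was over before study drug was taken. The SAP uses that information when only the day is unknown and ignores it when less of the start date is known. Two kinds of AE known to be pre-treatment can therefore enter the TEAE tables instead of the pre-treatment AE table that SAP 11.1 also lists.

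Such records can arise. Protocol 11.1 states: "All AEs will be recorded by the Investigator from the time the subject signs informed consent". Screening runs for up to 56 days before randomization (Protocol 4.1.1), and medications taken in the 56 days before randomization are recorded (Protocol 6.1.5).

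At stake is the accuracy of early safety tabulations. Protocol 1.4.1 reports that most deaths on oral azacitidine fell in the first 56 days of treatment, so events wrongly added to Cycles 1-2 land where readers will look hardest. SAP 5.1.1 keeps listings as recorded, so a listing could show an AE ending before first dose that the summary table counts as treatment-emergent.

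**Working it through.** The documents give no figure to reproduce here. The check is to apply the rules as written to test records.

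**1. Does the stop-date check reach the other cases?** In 18.1.1 it is a bullet under the day-only case. In 18.1.2 (subsequent MDS treatment) the same bullet again sits under the day-only case and is followed by another day-only bullet, so there it cannot be a closing rule for all cases. The stop-date half of 18.1.1 shows how a general rule is placed: in the heading. That heading rule does not help, because it alters only an imputed stop date and here the stop date is known.

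**2. Does a later definition catch the record?** No. SAP 11.1 uses onset date alone.

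**3. Test records.** The dates are illustrative assumptions: first dose 15 Jun 2015, last dose 1 Mar 2016. Duration = stop − start + 1.

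| Recorded start | Recorded stop | Start as written | TEAE if an AE | Prior if a medication | Duration | Start if the check covered all partial dates |
|---|---|---|---|---|---|---|
| 2015 | 20 May 2015 | 15 Jun 2015 | yes | no | −26 + 1 = −25 days | 20 May 2015 (not TEAE; prior; 1 day) |
| Jun 2015 | 10 Jun 2015 | 10 Jun 2015 | no | yes | 1 day | unchanged |
| May 2015 | 20 May 2015 | 20 May 2015 | no | yes | 1 day | unchanged |
| 2014 | 1 Nov 2014 | 31 Dec 2014 | no | yes | −60 + 1 = −59 days | 1 Nov 2014 |
| none | 20 May 2015 | none assigned | yes, by direct rule | no rule stated | – | needs its own sentence |

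Row 1 is the error by imputation, and row 5 is the error by direct rule. Rows 2 and 3 show the existing check working. Row 4 stays on the correct side of first dose but has a start after its stop.

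**4. Effect of row 1 on the AE tables.** Cycle 1 starts on the first-dose date (SAP 5.1.3), so the event falls in Cycles 1-2 and cycle days 1-7 (SAP 11.1.1). For the exposure-adjusted incidence rate (SAP 11.1), exposure of a subject with the event runs from first dose to event start inclusive:

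- with the false event: 15 Jun 2015 − 15 Jun 2015 + 1 = 1 day;
- without it, with no other event of that term and no death: (1 Mar 2016 + 28 days) − 15 Jun 2015 + 1 = 29 Mar 2016 − 15 Jun 2015 + 1 = 289 days.

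The numerator for that term gains 1 and the denominator loses 288 days for that subject. Row 5 has no onset date, so the text implies neither the cycle placement nor the 1-day exposure.

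**5. Effect of row 1 on a medication.** A start on 15 Jun 2015 is not before first dose, so the record is no longer prior. Under SAP 8.10 it is concomitant if a start on the day of initiation counts as after initiation. Read strictly, it meets neither part of that definition and falls in no class.

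**The case against.** The other side has several good points.

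- **Rarity.** SAP 5.1.1 expects log dates to be complete unless the item is ongoing, and Protocol 15.2 provides edit checks and queries to sites. A prospectively recorded screening AE with an exact stop date and only a year for its start should be unusual. If the stop is in January of the first-dose year, the month of a same-year start is known by deduction; once it is entered, the day-only check applies. This limits the count but does not remove the error: in row 1 the start month could be any from January to May.
- **Conservatism.** Counting an AE of doubtful timing as treatment-emergent is a defensible default, in line with imputing a missing relationship as related (SAP 11.1). That holds where timing is unknown. With a known stop before first dose there is no doubt left to resolve.
- **Balance.** These are pre-dose records in a randomized double-blind trial, so no systematic difference between arms is expected, and the AE tables are descriptive. This stands.
- **Intent.** The check may have been meant for all cases. Its placement in both 18.1.1 and 18.1.2 argues against reading it that way, and a programmer following the text would not apply it more widely.

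A reader might infer that washed-out prohibited drugs will appear as concomitant use. The documents do not support that. A start in any earlier year stays prior, SAP 8.10 does not clearly place a start on the first-dose day, and prior MDS treatments have their own case report forms whenever they stopped (Protocol 9) and their own table (SAP 8.4).

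**Conclusion.** The rule gives a wrong result in a narrow set of cases and should be corrected. Read literally, it misclassifies:

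- AEs with a year-only start in the first-dose year and a known stop before first dose, which become TEAEs by imputation;
- AEs with a fully missing start and a known stop before first dose, which become TEAEs by direct rule;
- medications with a year-only start in the first-dose year and a pre-dose stop, which lose prior status and may or may not become concomitant.

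Two wider readings should be resisted. Not every year-only start with a pre-dose stop is misclassified: an earlier-year start goes to 31 December, remains pre-treatment, and suffers only an impossible order of dates. Fully missing starts are not placed on Cycle 1 Day 1, since they receive no date.

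The documents do not say how many such records exist, and no percentage can be drawn from them. The number is probably very small. The primary endpoint and overall survival do not use these dates, so neither is affected. The conclusion assumes that the analysis program follows the text as placed; a program that already applies the check to every start date would avoid the imputation error but still need the rule for fully missing starts. This is a minor point.

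**What to change.** In SAP 18.1.1, move the existing stop-date check from the day-only case to the heading for incomplete start dates, so that it covers every partial start date. Add one sentence: if the start date is fully missing and the known stop date is before first dose, the record is pre-treatment (AE) or prior (medication). Leave the present rule for all records whose stop date is missing or falls on or after first dose.

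The cost is a sentence or two and a small code change. Protocol Amendment 6.0 states that the primary clinical study report is final, so the practical steps are to see how the program handled these records, count any with a stop before first dose that were tabulated as TEAEs, and use the corrected rule in any later reporting.

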18.1.2. Impute Missing Start Dates of Subsequent MDS Treatment

If the start date of the subsequent MDS treatment is unknown, it will be imputed as the earliest possible date after the last dose date (1 day after) which is collected in the treatment discontinuation CRF.

Missing day and month

- If the year is **same** as the year of the last dose date, then the last dose date + 1 day will be assigned to the missing date.
- If the year is **after** the year of the last dose date, then January 1 will be assigned to the missing fields.
- The year should not be **prior to** the year of the last dose date. In case that happens, December 31 will be assigned to the missing fields.

Missing day only

- If the month and year are **same** as the year and month of the last dose date, then the last dose date + 1 day will be assigned to the missing date.
- If the month and year are **after** the year and month of the last dose date, then the first day of the month will be assigned to the missing day.
- If the stop date is non-missing and the imputed start date is after the stop date, the start date will be imputed by the stop date.
- The month and year should not be **prior to** the year and month of the last dose date. In case that happens, the last day of the month will be assigned to the missing day.

Missing day, month, and year

- The start date of the post MDS treatment should not be completely missing. In case that happens, the last dose date + 1 day will be assigned to the missing date.

18.2. Appendix B: Myelodysplastic Syndromes World Health Organization Classification System

Myelodysplastic Syndromes WHO Classification System		
Category	Definition	
	Peripheral Blood Smear Evaluation	Bone Marrow Evaluation
Refractory cytopenia with unilineage dysplasia (RCUD): (refractory anemia [RA]; refractory neutropenia [RN]; refractory thrombocytopenia [RT])	Unicytopenia or bicytopenia ^a No or rare blasts (< 1%) ^b	Unilineage dysplasia: ≥ 10% of the cells in one myeloid lineage < 5% blasts < 15% of erythroid precursors are ringed sideroblasts
Refractory Anemia With Ringed Sideroblasts (RARS)	Anemia No blasts	≥ 15% of erythroid precursors are ringed sideroblasts Erythroid dysplasia only < 5% blasts
Refractory Cytopenia With Multilineage Dysplasia (RCMD)	Cytopenia(s) No or rare blasts (< 1%) ^b No Auer rods < 1x10 ⁹ /L monocytes	Dysplasia in ≥ 10% of the cells in ≥ 2 myeloid lineages (neutrophil and/or erythroid precursors and/or megakaryocytes) < 5% blasts in marrow No Auer rods ± 15% ringed sideroblasts
Refractory Anemia With Excess Blasts-1 (RAEB-1)	Cytopenias < 5% blasts ^b No Auer rods < 1x10 ⁹ /L monocytes	Unilineage or multilineage dysplasia 5%-9% blasts ^b No Auer rods
Refractory Anemia With Excess Blasts-2 (RAEB-2)	Cytopenias 5%-19% blasts ^c Auer rods ^c < 1x10 ⁹ /L monocytes	Unilineage or multilineage dysplasia 10%-19% blasts ^c Auer rods ± ^c
Myelodysplastic Syndrome - Unclassified (MDS-U)	Cytopenias < 1% blasts ^b	Unequivocal dysplasia in < 10% of cells in one or more myeloid lineages when accompanied by a cytogenetic abnormality considered as presumptive evidence for a diagnosis of MDS ^d
MDS Associated With Isolated del(5q)	Anemia Usually normal or increased platelet count No or rare blasts (< 1%)	Normal to increased megakaryocytes with hypolobated nuclei < 5% blasts Isolated del(5q) cytogenetic abnormality No Auer rods

^a Bicytopenia may occasionally be observed. Cases with pancytopenia should be classified as MDS-U.

^b If the marrow myeloblast percentage is < 5% but there are 2% to 4% myeloblasts in the blood, the diagnostic classification is RAEB-1. Cases of RCUD and RCMD with 1% myeloblasts in the blood should be classified as MDS-U.

^c Cases with Auer rods and < 5% myeloblasts in the blood and less than 10% in the marrow should be classified as RAEB-2. Although the finding of 5% to 19% blasts in the blood is, in itself, diagnostic of RAEB-2, cases of RAEB-2 may have 5% blasts in the blood if they have Auer rods or 10% to 19% blasts in the marrow or both. Similarly, cases of RAEB-2 may have < 10% blasts in the marrow but may be diagnosed by the other 2 findings, Auer rods + and/or 5% to 19% blasts in the blood.

^d Includes unbalanced abnormalities -7 or del(7q), -5 or del(5q), i(17q) or t(17p), -13 or del(13q), del(11q), del(12p) or t(12p), del(9q), idic(X)(q13), balanced abnormalities t(11;16)(q23;p13.3), t(3;21)(q26.2;q22.1), t(1;3)(p36.3;q21.1), T2;11(p21;q23), inv(3)(q21q26.2), and t(6;9)(p23;q34), and complex karyotype (3 or more

chromosomal abnormalities) involving one of more of the listed abnormalities.

Sources: Brunning RD, Bennett JM, Flandrin G, Matutes E, Head D, Vardiman JW, et al. Pathology and genetics of tumors of hematopoietic and lymphoid tissues. In: Jaffe ES, Harris NL, Stein H, Vardiman JW, editors. World Health Organization Classification of Tumors. Lyon (France). IARC Press, 2001:63-73.

CELGENE PROPRIETARY INFORMATION

